7.3.3. Advanced Solid Malignancy Only Assessments

Patient response will be assessed by the procedures described in the following subsections and graded according to RECIST 1.1 ([Appendix 4](#)).

7.3.3.1. CT, MRI, PET-CT, or Imaging Methodology Per Investigator Discretion

Disease response is based on tumor measurement using computed tomography (CT) scans or, magnetic resonance imaging (MRI) scans, or PET-CT, or imaging methodology per Investigator discretion. Scans will be performed at Screening (Day -30 to Day -1), then every 8 weeks \pm 7 days (e.g., Day 1 of odd numbered cycles) until disease progression or the EoT visit. EoT scan is only required for patients who end treatment for reasons other than disease progression.

The same scan modality should be used for all assessments.

7.4. Pharmacokinetic Assessments

7.4.1. PK Sampling for KPT-9274

Parts A and B

PK sampling will be performed in all patients receiving KPT-9274.

- PK samples will be collected for all patients at PK time points listed in [Table 17](#) except on C1D24 at 4, 12, 18, and 32 hours post-dose; PK samples on C1D24 at 4, 12, 18, and 32 hours post-dose will only be collected for the first 18 patients enrolled in the expansion phase (see Section [3.1](#)).

Blood draws (using 2 mL/K₂EDTA purple top tubes) for PK analysis will be performed as described in [Table 17](#).

Details of PK sample collection and processing can be found in the *Laboratory Manual*.

Plasma samples will be analyzed via validated high performance liquid chromatography/tandem mass spectrometry (HPLC/MS-MS) methods for plasma KPT-9274 concentrations.

PK parameters may include, but are not limited to, estimations of C_{max}, AUC, t_{max}, t_{1/2}, V_d/F, and CL/F.

Patients must attend the clinic for PK sampling that occurs on non-dosing days.

If the dose is missed, PK blood draws will not be collected on that day.

If a patient's dose is changed, blood sampling for PK (as requested for C1D1) should be repeated on the first day of dose change at the same time points as described for C1D1, C1D2, and C1D3.

[figure not shown]
If a patient experiences an AE that fits the criteria of a DLT as determined by the Investigator in either the Dose Escalation or Dose Expansion Phase, an unscheduled PK blood sample should be collected for measurement of drug concentrations. If a patient experiences a study treatment-related AE that fits the criteria of a SAE or discontinues from the study treatment due to study treatment related toxicities, an unscheduled PK blood sample must be obtained as soon as possible after the last dose of KPT-9274 and the date and time of last dose recorded.

Additionally, if at any time during the study a QTc >500 msec has been demonstrated by 12-lead ECG, then an unscheduled PK draw should be obtained as close to the time of the repeat ECG as possible.

Part C

Starting from Cycle 1 Day 1 (C1D1), blood will be drawn at 0 h (< 15 mins prior to dosing), 3 h \pm 15 mins, 6 h \pm 30 mins, 8 h \pm 30 mins, 24 h \pm 60 mins, and 48 h \pm 60 mins. Cycle 2 Day 1 (C2D1), blood will be drawn at 0 h (< 15mins prior dosing), 3 h \pm 15 mins, , 6 h \pm 30 mins, 8 h \pm 30 mins, 24 h \pm 60 mins, and 48 h \pm 60 mins after C2D1 dose. Time since last meal and a description of the meal contents will be reported by the patient to the treating physician prior to each PK blood draw. PK assessments are outlined in [Table 18](#).

CCI

CCI

[figure not shown]

Table 17: Collection Time Points and Sample Volumes for PK and CCI for Parts A and B

Time Point	Total Volume of Blood (mL)	Number of Tubes by Volume of Blood		Biopsy
		PK	CCI	
		1 tube x 2.0 mL		
Screening				
Between D -30 and D 7	--	--		2 fresh biopsies and 1 formalin fixed biopsy
C1D1 (repeat if patient dose changes)				
Pre-dose (< 10 min before KPT-9274 dosing)	13	X		--
0.5 hr (\pm 5 min) post-dose	2	X		--
1 hr (\pm 10 min) post-dose	2	X		--
2 hr (\pm 10 min) post-dose	2	X		--
4 hr (\pm 20 min) post-dose	13	X		--
8 hr (\pm 30 min) post-dose	13	X		--
C1D2 (repeat if patient dose changes)				
24 hr (\pm 2 hours) after intake of first dose on C1D1	13	X		--
C1D3 (repeat if patient dose changes)				
48 hr (\pm 2 hours) after intake of first dose on C1D1, prior to C1D3 dose	13	X		--
C1D8				
Pre-dose (< 10 min before KPT-9274 dosing)	13	X		--
2 hr (\pm 10 min) post-dose	2	X		--
C1D15				

Time Point	Total Volume of Blood (mL)	Number of Tubes by Volume of Blood		Biopsy
		PK	CCI	
Pre-dose (< 10 min before KPT-9274 dosing)	13	X		--
2 hr (\pm 10 min) post-dose	2	X		--

Time Point	Total Volume of Blood (mL)	Number of Tubes by Volume of Blood		Biopsy
		PK	CCI	
		1 tube x 2.0 mL		Lymph Node Biopsy and/or Tumor Biopsy
C1D24				--
Pre-dose (< 10 min before KPT-9274 dosing)	13	X		--
2 hr (\pm 10 min) post-dose	2	X		--
4 hr (\pm 20 min) post-dose (Expansion Phase only) ²	2	X		--
8 hr (\pm 30 min) post-dose	13	X		--
12 hr (\pm 60 min) post-dose (Expansion Phase only) ²	2	X		--
18 hr (\pm 60 min) post-dose (Expansion Phase only) ²	2	X		--
C1D25				--
24 hr (\pm 2 hours) after intake of dose on C1D24	13	X		--
32 hr (\pm 2 hours) after intake of dose on C1D24 (Expansion Phase only) ²	2	X		--
C1D26				2 fresh biopsies and 1 formalin fixed biopsy ¹
48 hr (\pm 2 hours) after intake of dose on C1D24, prior to C1D26 dose	13	X		--
1 hr (\pm 10 min) post-dose	2	X		--
2 hr (\pm 10 min) post-dose	2	X		--
4 hr (\pm 20 min) post-dose	13	X		--
8 hr (\pm 30 min) post-dose	13	X		--

Time Point	Total Volume of Blood (mL)	Number of Tubes by Volume of Blood		Biopsy
		PK	CCI	
		1 tube x 2.0 mL		Lymph Node Biopsy and/or Tumor Biopsy
C2D15				--
Pre-dose (< 10 min before KPT-9274 dosing)	2	X		--
2 hr (\pm 10 min) post-dose	2	X		--
C3D1				--
Pre-dose (< 10 min before KPT-9274 dosing)	13	X		--
2 hr (\pm 10 min) post-dose	2	X		--
24 hr (\pm 2 hours) after intake of first dose on D1	13	X		--
Day 1 of Cycle 5 and Beyond Odd Cycles Only				--
Pre-dose (< 10 min before KPT-9274 dosing)	13	X		--
24 hr (\pm 2 hours) after intake of first dose on D1	13	X		--
Cycle 6 Day 1 and/or at the time of progression				--
\pm 7 days	--			2 fresh biopsies and 1 formalin fixed biopsy ¹
End-of-therapy				--
\pm 7 days	13	X		--

¹ For the biopsies on C1D26 (\pm 7 days) and C6D1 (\pm 7 days), patients will be allowed to continue treatment if: 1) a patient refuses the biopsy, 2) in the opinion of the treating physician or physician performing the biopsy that the biopsy will pose significant risk to the patient, or 3) if the biopsy sample obtained on first attempt is not adequate.

[figure not shown]
² PK samples at these time points will only be collected for the first 18 patients enrolled in the expansion phase (see Section 3.1).

Table 18: Collection Time Points and Sample Volumes for PK and CCI for Part C

Time Point	Total Volume of Blood (mL)	Number of Tubes by Volume of Blood		Biopsy
		PK	CCI	
		1 tube x 2.0 mL		
Screening				
Between D -30 and D -1	--	--		2 fresh biopsies and 1 formalin fixed biopsy
C1D1				
Pre-dose (< 15 min before KPT-9274 dosing)	4.5	X		--
3 hr (\pm 15 min) post-dose	2	X		--
6 hr (\pm 30 min) post-dose	2	X		--
8 hr (\pm 30 min) post-dose	2	X		--
C1D2				
24 hr (\pm 60 min) after intake of first dose on C1D1	2	X		--
C1D3				
48 hr (\pm 60 min) after intake of first dose on C1D1, prior to C1D3 dose	2	X		--
C2D1				
Pre-dose (< 15 min before KPT-9274 dosing)	4.5	X		2 fresh biopsies and 1 formalin fixed biopsy ¹
3hr (\pm 15 min) post-dose	2	X		--
6 hr (\pm 30 min) post-dose	2	X		--
8 hr (\pm 30 min) post-dose	2	X		--
24 hr (\pm 60 min) after intake of first dose on D1	2	X		--
48 hr (\pm 60 min) after intake of first dose on D1	2	X		--
End-of-therapy				2 fresh biopsies and 1 formalin fixed biopsy ¹

1. For the biopsies on C2D1 (\pm 7 days) and EoT (\pm 7 days), patients will be allowed to continue treatment if: 1) a patient refuses the biopsy, 2) in the opinion of the treating physician or physician performing the biopsy that the biopsy will pose significant risk to the patient, or 3) if the biopsy sample obtained on first attempt is not adequate.

CCI

CCI

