2.1.2. Secondary Objectives

Parts A and B

Dose Escalation

- To define the preliminary evidence of anti-tumor activity of KPT-9274 alone (Part A) and with co-administration of niacin ER (Part B) in patients with advanced solid malignancies or NHL.

Dose Escalation and Dose Expansion

[figure not shown]
- To determine the pharmacokinetic (PK) profile of KPT-9274, including, but not limited to, maximum plasma concentration, time-to-peak plasma concentration, terminal half-life, and plasma clearance.

Part C

- To determine the preliminary evidence of anti-tumor activity of KPT-9274 + nivolumab in patients with melanoma.
- To characterize the PK of KPT-9274 when administered with nivolumab in patients with melanoma.

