6.2.3. Dosing Information

Patients will receive oral KPT-9274 three times a week every other day (Days 1, 3, 5, 8, 10, 12, 15, 17, 19, 22, 24, and 26) during each 28-day cycle.

Study treatment will be administered in the clinic and at home as indicated in [Table 4](#). Study treatment dosing will occur in the clinic during Cycle 1 on Days 1, 3, 8, 15, 22, 24, and 26, during Cycle 2 on Days 1, 8, 15, and 22, and during \geq Cycle 3 on Days 1 and 15. Study treatment dosing will occur at home during Cycle 1 on Days 5, 10, 12, 17, and 19, during Cycle 2 on Days 3, 5, 10, 12, 17, 19, 24, and 26 and during Cycles \geq 3 on Days 3, 5, 8, 10, 12, 17, 19, 22, 24, and 26.

During Part B of the Dose Escalation Phase, patients will receive 500 mg niacin ER co-administered with each dose of KPT-9274. The starting dose of 500 mg niacin ER may be titrated to 2,000 mg of daily dose, per label. The starting dose for KPT-9274 in Part B will be a dose and schedule that cleared DLT assessment during Part A. For the purposes of dose escalation decisions, a standard 3+3 dose escalation design will be used during both Part A and Part B.

A total of ~65 patients with advanced solid malignancies and NHL may be enrolled to further explore safety, tolerability and preliminary evidence of anti-tumor activity of the RP2D of KPT-9274 \pm niacin ER. After declaring the RP2D \pm niacin ER (see Section [6.2.6](#)), based on the safety and tolerability results of the Dose Escalation Phase, a decision will be made whether expansion (4 groups, ~45 patients total) will be conducted at the RP2D of KPT-9274 single agent or at the RP2D of KPT-9274 + niacin ER. If the 45 patient expansion is conducted at the RP2D of KPT-9274 + niacin ER, an optional expansion with < 20 patients at the RP2D of KPT-9274 single agent may be initiated. Futility analyses based on clinical efficacy will be conducted in a maximum of 10 patients dosed at the RP2D \pm niacin ER (see Section [6.2.7](#) for additional details).

Dose escalation will occur according to the Dose Escalation Guidelines provided in Section [6.2.6](#).

Patients with melanoma enrolled in Part C, KPT-9274 + nivolumab, cohort will receive nivolumab (480 mg once per 28 day cycle) according to the current prescribing information.

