6.2.6.2. Dose-Limiting Toxicity

A DLT is defined as an AE or abnormal laboratory value that occurs within the first 28 days of treatment with KPT-9274, except for those that are clearly and incontrovertibly due to underlying disease, disease progression, or extraneous causes, and meets any of the criteria included in [Table 14](#). The CTCAE, Version 4.03 will be used for grading. In addition, > 3 missed (consecutive or non-consecutive) doses of KPT-9274 in the first 28 days due to a drug related toxicity will be considered to be a DLT.

Other events may occur which do not meet the definition of a DLT, but are of concern to the Investigators and Karyopharm, and may then be considered to be DLTs.

Table 14: Criteria for Defining Dose-Limiting Toxicities

Toxicity	Any of the following criteria (based on CTCAE [Version 4.03]):
Non-Hematologic	Grade \geq 3 nausea/vomiting, dehydration or diarrhea while taking optimal supportive medications.
	Any other Grade \geq 3 non-hematological toxicity except alopecia or electrolyte abnormalities correctable with supportive therapy.
Hematologic	Grade 4 neutropenia lasting more than 5 days.
	Febrile neutropenia of any duration (ANC $< 1.0 \times 10^9$ with single temperature $> 38.3^{\circ}\text{C}$ or a sustained temperature $\geq 38^{\circ}\text{C}$ for more than 1 hour).
	Grade 4 thrombocytopenia, or Grade 3 thrombocytopenia with bleeding, or any requirement for platelet transfusion.
	Grade 4 anemia, unexplained by underlying disease.

CTCAE Version 4.03 will be used for grading AEs and laboratory abnormalities. Patients may receive supportive care as per local institutional guidelines.

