9.6. Pharmacokinetic Analysis

PK Parameters for KPT-9274 will be determined following administration of KPT-9274 (Section 7.4).

[figure not shown]
KPT-9274 PK parameters may include, but are not limited to, C_{max} , AUC, t_{max} , $t_{1/2}$, V_d/F , and CL/F . Interim PK analyses may be performed throughout the study on draft, unaudited plasma KPT-9274 concentration data.

The PK properties of KPT-9274 will be evaluated and data collected over time will be summarized. PK endpoints will be computed using non-compartmental methods. Summary statistics such as mean, standard deviation, median, range, etc., will be compiled and reported. A separate Data Analysis Plan (DAP) might be prepared prior to initiation of the final PK analysis.

CCI

CCI

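### In Parts A and B, the missed-dose rule for PK draws, read literally, also cancels the 48 h sample of the previous dose when the C1D3 or C1D26 dose is missed

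*Protocol*

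**What the plan says.** Protocol Section 7.4.1 (Parts A and B) and footnote 16 to the schedules of assessments both say: "If the dose is missed, PK blood draws will not be collected on that day". The rule follows the calendar day. It makes no exception for samples that belong to an earlier dose.

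Table 17 schedules two 48 h samples, and both fall on dosing days:

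- C1D3: the sample is due 48 h "after intake of first dose on C1D1, prior to C1D3 dose". It is the only PK draw listed for that day.
- C1D26: the first sample is due 48 h "after intake of dose on C1D24, prior to C1D26 dose". The later draws that day (1, 2, 4 and 8 h) follow the C1D26 dose itself.

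The C1D1 to C1D3 draws are repeated if the patient's dose changes. Section 7.4.1 also requires attendance for PK draws on non-dosing days, without saying whether a dosing day with a missed dose counts as one.

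The PK profile is a secondary objective (Section 2.1.2) and covers "maximum plasma concentration, time-to-peak plasma concentration, terminal half-life, and plasma clearance". Section 9.6 adds: "PK endpoints will be computed using non-compartmental methods". Section 9.3.4 admits patients with adequate sampling to the PK population but does not define it. The SAP leaves PK methods to a separate plan.

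**The concern.** A 48 h sample drawn before that day's dose needs only the earlier dose to have been taken. Missing the new dose does not spoil it. On C1D3 the rule therefore has a single effect, which is to discard a valid sample. On C1D26 it correctly removes the four post-dose draws but takes the 48 h sample with them.

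That sample is the last of its profile, and a non-compartmental half-life depends most on the late points. Clearance depends on total AUC, which depends on how much must be extrapolated past the last sample. Sections 6.2.6.1 and 6.2.6.3 also let available PK data inform dose-escalation decisions. Because the rule and Table 17 can be read differently, sites may also act differently on the same event.

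**Working it through.** The documents state no figure for this point, so there is none to reproduce.

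**Inputs from the documents**

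- Days 1, 3, 24 and 26 are dosing days (Section 6.2.3). Day 1 to Day 3 and Day 24 to Day 26 are each 2 × 24 = 48 h.
- C1D1 profile (Table 17): pre-dose, 0.5, 1, 2, 4, 8, 24 and 48 h.
- C1D24 profile (Table 17): pre-dose, 2, 8, 24 and 48 h. The first 18 expansion patients also have 4, 12, 18 and 32 h.

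**Assumptions**

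- Peak near 4 h. The only source is an estimated value in the rationale for Amendment 1.0 (Appendix 6), so 2 h is also tried.
- Half-life is not given; 6 to 24 h is shown.
- Single-exponential decline after the peak, with equal error on the log scale.

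**Step 1: precision of the terminal slope.** In a log-linear fit the standard error is proportional to 1/√Sxx, where Sxx = Σ(t − mean t)². The ratio without to with the 48 h sample is √(Sxx with / Sxx without).

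- C1D1, peak at 4 h. With 8, 24, 48 h: mean 26.67, Sxx = 348.4 + 7.1 + 455.1 = 810.7. With 8, 24 h: mean 16, Sxx = 64 + 64 = 128. Ratio √(810.7/128) = 2.5. Points fall from 3 to 2, and two points leave no residual degree of freedom.
- C1D1, peak at 2 h. With 4, 8, 24, 48 h: Sxx = 1196. With 4, 8, 24 h: Sxx = 224. Ratio 2.3. Points fall from 4 to 3.
- C1D24 without the extra samples. Highest value at 2 h: 3 points fall to 2, ratio 2.5. Highest value at 8 h: 2 points fall to 1, and no slope can be fitted.
- C1D24, first 18 expansion patients, peak at 4 h. With 8, 12, 18, 24, 32, 48 h: Sxx = 1075.3. Without 48 h: Sxx = 364.8. Ratio 1.7. Points fall from 6 to 5.

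**Step 2: AUC extrapolated beyond the last sample.** The share is 2^(−t_last / half-life).

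| Assumed half-life | Last sample 48 h | Last sample 24 h |
|---|---|---|
| 6 h | 2^−8 = 0.4% | 2^−4 = 6% |
| 8 h | 2^−6 = 1.6% | 2^−3 = 12.5% |
| 12 h | 2^−4 = 6% | 2^−2 = 25% |
| 24 h | 2^−2 = 25% | 2^−1 = 50% |

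This is single-dose arithmetic, so it applies directly to C1D1. On C1D24 the missing sample is the one that closes the 48 h dosing interval.

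**Step 3: illustration on the half-life scale.** With an assumed log-scale error of 0.2 and a true half-life of 12 h, simulated estimates (5th to 95th percentile) run from 10.0 to 15.0 h using 8, 24 and 48 h, and from 8.0 to 24.1 h using 8 and 24 h.

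**Step 4: reach.** Only a dose missed on C1D3, on C1D26, or on the 48 h day of a repeat profile removes a 48 h sample. Table 17 lists no other.

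**The case against.** The strongest case against is that this is a drafting ambiguity with limited effect. A patient who misses C1D26 normally already has the full C1D1 profile. A patient who misses C1D3 and resumes still gets the C1D24 to C1D26 profile. The first 18 expansion patients keep C1D24 samples to 32 h. With a 2 h peak, C1D1 keeps three post-peak points. A separate PK plan may set its own rules. All of this stands and limits the size of the point. It does not make the sentence agree with Table 17, and a repeat profile has the same flaw if its 48 h day falls on a missed dose.

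Stronger readings that a reader might infer, and why they fail:

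- *Patients held for toxicity lose half-life and clearance.* Only the days in Step 4 matter, and usually one profile survives.
- *The truncated profile cannot be reported.* That needs a minimum-points rule, which the documents do not give, and a peak time known only as an estimate.
- *Holds are common, since Grade 3-4 related anemia occurred in 22 + 1 = 23 of 47 patients (Table 11).* That count is not restricted to Cycle 1, and Table 16 makes holding for anemia a matter of consideration. It is not a hold rate.
- *The loss biases half-life short and clearance high.* Section 1.2.1 links adverse events to dose level. It does not show that, at a given dose, patients who miss doses have higher exposure.
- *The toxicity-triggered sample is a failed backup and should be triggered earlier.* For a DLT, "an unscheduled PK blood sample should be collected for measurement of drug concentrations", with no time window. For the route in which more than three missed "doses of KPT-9274 in the first 28 days due to a drug related toxicity will be considered to be a DLT", four consecutive misses put recognition 216 to 240 h after the last dose. But nothing describes that sample as a substitute for the 48 h point. A separate clause requires a sample as soon as possible after the last dose for a related SAE or discontinuation for related toxicity, and Section 6.2.8 makes a Cycle 1 escalation DLT a discontinuation. Triggering at the first withheld dose could require unscheduled visits on home-dosing days, a debatable trade-off. It is true that a hold meeting none of these triggers brings no replacement sample, which is a reason to keep the 48 h draw.

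**Conclusion.** The point holds in a limited form. As written, the rule discards a valid terminal-phase sample whenever the dose is missed on C1D3, on C1D26, or on the 48 h day of a repeat profile, and the sentence on non-dosing days does not clearly override it. The affected profile then ends at 24 h, or 32 h on C1D24 for the first 18 expansion patients. Half-life and clearance from it are at risk of being imprecise or non-estimable.

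The size rests on the assumed peak, half-life and single-exponential decline: the slope's standard error rises by a factor of about 2.5 with a 4 h peak on C1D1, and at a 6 h half-life the extrapolated share stays small (6%). How many patients are affected cannot be stated, because the documents give no rate of missed doses on these days. The missed-dose rule stands under Parts A and B, and the Part C text does not repeat it.

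**What to change.** Replace the sentence in Section 7.4.1 and in footnote 16 with:

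*If a dose is missed, the PK samples timed from that dose are not collected. Samples timed from an earlier dose that was taken (C1D3 48 h after C1D1; C1D25 24 h, and 32 h where applicable, and C1D26 48 h after C1D24; and the corresponding samples of a repeat profile) are collected at their nominal time even if that day's dose is missed.*

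This also makes clear that no C1D25 or C1D26 sample is timed from a C1D24 dose that was never taken. The cost is one sentence changed in two places at the next amendment. It adds no scheduled draw and changes nothing about dosing. A patient whose C1D3 or C1D26 dose is missed would still attend that scheduled visit for the draw. The trigger for the unscheduled sample can stay as it is.

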This Arm will treat approximately 20 patients with melanoma who progressed on an anti-PD-1 or anti-PD-L1 antibody in a prior line of therapy. Two dose levels of KPT-9274 (30 and 40 mg) in combination with nivolumab will be tested in parallel. Patients will be enrolled first into the 30 mg cohort. Patients will be treated with 30 or 40 mg KPT-9274 three times a week every other day (Days 1, 3, 5, 8, 10, 12,

15, 17, 19, 22, 24, and 26) during each 28-day cycle in combination with a standard dose and schedule of nivolumab (480 mg on Day 1 of each 28-day cycle). A maximum of 10 patients may be enrolled at each dose level. Treatment will continue until disease progression, unacceptable AEs or toxicity that cannot be managed by supportive care, patient's withdrawal of consent, Investigator decision to discontinue study treatment, pregnancy, death, or Sponsor decision to terminate the study. A safety review committee will evaluate all available data from both cohorts after the last patient enrolled has been observed for at least 2 cycles to determine the RP2D. Additional dose levels (20 mg or 60 mg) might be evaluated if an optimal dose is not identified and the safety review committee is in agreement. The definition of a DLT is the same as described in Parts A and B. Response will be assessed every 8 weeks per RECIST 1.1 criteria.

KPT-9274 Dose Finding (Part C)

Cohort	KPT-9274	Nivolumab
	Days 1, 3, 5, 8, 10, 12, 15, 17, 19, 22, 24, 26 in a 28-day cycle	Day 1 in a 28-day cycle
1	30 mg	480 mg
2	40 mg	480 mg

Pharmacokinetic CCI Samples

Blood samples for pharmacokinetic (PK) and CCI assessments will be collected during both the Dose Escalation and Dose Expansion Phases of the study. Biopsies for Part C will be collected at baseline and at the first response assessment.

Number of Patients (planned):

Approximately 175 patients may be enrolled. However, the number of patients required for completion of study enrollment cannot be defined *a priori* since this depends on the number of patients needed for the dose escalations in Parts A and B. Assuming that 9 dose levels of KPT-9274 are evaluated during both Part A (KPT-9274 single agent) and Part B (KPT-9274 + niacin ER) of the Dose Escalation Phase and up to 65 additional patients are enrolled in the Dose Expansion Phase the total combined enrollment is estimated to be 175 patients.

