Telephone contact ¹²		X	X		X	X		X	X		X	X

Visit Type	Cycle 2						Cycle 3 and Beyond					
	Week 1		Week 2	Week 3		Week 4	Week 1	Week 2		Week 3		Week 4
	D1	D4 ±1 day	D11 ±1 day	D15	D18 ±1 day	D25 ±1 day	D1	D4 ±1 day	D11 ±1 day	D15	D18 ±1 day	D25 ±1 day
Clinic Visit	Clinic Visit	Phone Call	Phone Call	Clinic Visit	Phone Call	Phone Call	Clinic Visit	Phone Call	Phone Call	Clinic Visit	Phone Call	Phone Call
Tumor biopsy ¹⁹							X ±7 days					
CT, MRI, PET-CT, imaging methodology per investigator discretion ²⁰							X (±7 days; odd cycles only)					
Study treatment dosing in-clinic ¹⁴	See Table 8											

Table 7: Schedule of Assessments for End-of-Treatment and Beyond (Part C)

Activity/Assessment	End-of-Treatment (EoT) Visit		Safety Follow-up Call ¹⁶	Durability of Response and Survival Follow-up ¹³
	≤ 14 Days Post Last Dose		30 Days Post-Last Dose	Every 3 months for 1 year after the safety follow-up call
	+ 7 days	± 7 days		
Clinical Assessments				
Patient weight	X			
Vital Signs (BP, pulse, temp) ⁴	X			
Complete physical exam	X			
12-lead ECG ⁵	X			
ECOG	X			
Hematology consultation, testing, and biopsy ¹⁷	As clinically indicated			
Clinical Labs				
CBC with differential	X			
TSH ⁹	X			
Complete serum chemistry	X			
Amylase and lipase ⁸	X			
Coagulation tests	X			
Serum hCG pregnancy test ⁹	X			
Vitamin B12, folate, iron, erythropoietin, haptoglobin, and transferrin levels and reticulocyte count ¹⁸	X (Optional) ¹⁸			

Activity/Assessment	End-of-Treatment (EoT) Visit	Safety Follow-up Call ¹⁶	Durability of Response and Survival Follow-up ¹³
	≤ 14 Days Post Last Dose	30 Days Post-Last Dose	Every 3 months for 1 year after the safety follow-up call
		+ 7 days	± 7 days
Adverse events	X	X	
Concomitant medications	X	X	
Telephone contact ¹²		X	X (If in person visit is not performed)
Antineoplastic therapy after EoT		X	X
Tumor biopsy ¹⁹	X		
CT, MRI, PET-CT, imaging methodology per investigator discretion ²⁰	X		X

Sites should adhere to the 28-day cycle.

Procedures to be performed during clinic visits will be done prior to the administration of study treatment on those days.

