- 16 Safety follow-up telephone call [30 days post-last dose (+ 7 days)] with patient after their last dose of study treatment to evaluate their overall medical condition and status of disease, AEs, including follow-up on any AEs that were not resolved at the EoT Visit, and collection of information on any antineoplastic therapies used after discontinuation of study treatment.
- 17 At the Investigator's discretion, in consultation with the Karyopharm Medical Monitor, patients with clinically significant hematological AEs, including any grade of treatment-emergent anemia or abnormal reticulocyte counts, may have a hematology consultation. Hematological testing (including but not limited to standard hematological evaluations and erythropoietin level) \pm bone marrow biopsy may be performed as clinically indicated per institutional standards.

18 Patients with treatment-emergent anemia should have blood levels of vitamin B12, folate, iron, erythropoietin, haptoglobin, and transferrin and reticulocyte counts assessed as soon as possible after onset. Patients with \leq Grade 1 anemia should have their levels/counts assessed no less than once a month and patients with \geq Grade 2 anemia should have their levels/counts assessed every 2 weeks.

19 For explorative analysis research procedure, tumor tissue will be obtained pre- treatment (Day -30 to Day 1) , C3D1 (\pm 7 days), and at the time of progression. Each biopsy will be divided into 3 portions, resulting in two fresh biopsies and one formalin fixed biopsy. *For the biopsies on C3D1 and EoT, patients will be allowed to continue treatment if: 1) a patient refuses the biopsy, 2) in the opinion of the treating physician or physician performing the biopsy that the biopsy will pose significant risk to the patient, or 3) if the biopsy sample obtained on the first attempt is not adequate.*

20 Advanced solid malignancies: CT, MRI, or PET-CT scans will be performed at screening (Day -30 to Day -1), then every 8 weeks \pm 7 days (e.g., Day 1 of odd numbered cycles), until disease progression or the EoT visit and Durability of Response and Survival Follow-up. EoT scan is only required for patients who end treatment for reasons other than disease progression. The same scan modality should be used for all assessments. Durability of Response and Survival Follow-up scan is only for patients who have not progressed.

[figure not shown]

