In Part C, a cohort of patients with melanoma that have progressed on an anti-PD1 or anti-PD-L1 antibody will be treated with KPT-9274 (at a dose that cleared DLT evaluation in Part A) + nivolumab. Two dose levels of KPT-9274 (30 and 40 mg) in combination with nivolumab will be tested in parallel. Patients will be enrolled first into the 30 mg cohort. Patients will be treated with 30 or 40 mg KPT-9274 three times a week every other day (Days 1, 3, 5, 8, 10, 12, 15, 17, 19, 22, 24, and 26) during each 28-day cycle in combination with a standard dose and schedule of nivolumab (480 mg on Day 1 of each 28-day cycle). A maximum of 10 patients may be enrolled at each dose level. Treatment will continue until disease progression, unacceptable AEs or toxicity that cannot be managed by supportive care, patient's withdrawal of consent, Investigator decision to discontinue study treatment, pregnancy, death, or Sponsor decision to terminate the study. A safety review committee will evaluate all available data from both cohorts after the last patient enrolled has been observed for at least 2 cycles to determine the RP2D.

Additional dose levels (20 mg or 60 mg) might be evaluated if an optimal dose is not identified and the safety review committee is in agreement. The definition of a DLT is the same as described in Parts A and B. Response will be assessed every 8 weeks per RECIST 1.1 criteria ([Appendix 4](#)).

All phases of the study will be comprised of Screening, Treatment, and Follow-up periods.

Screening will be performed within 30 or 14 days prior to the start of therapy (i.e., Day -30 to Day -1, Day -30 to Day -14, or Day -14 to Day -1), as summarized in [Table 1](#) and [Table 5](#). During the Treatment period, procedures are to be performed during clinic visits prior to the administration of study treatment on those days as presented in [Table 1](#), [Table 2](#), [Table 5](#) and [Table 6](#). The Follow-up period includes the EOT visit, the Safety Follow-up visit, and Durability of Response and Survival Follow-up; see [Table 3](#) and [Table 7](#) for assessments to be completed during the Follow-up period.

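### Part C gives two visits for the on-treatment tumor biopsy, Cycle 2 Day 1 and Cycle 3 Day 1, with windows that do not overlap

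*Protocol*

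**What the plan says.** Five places in the current protocol text fix the time of the Part C on-treatment biopsy.

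- **Table 18** (Section 7.4.1, Part C collection time points) has the entry "2 fresh biopsies and 1 formalin fixed biopsy ¹" on the Cycle 2 Day 1 pre-dose row. It has no Cycle 3 row.
- **Footnote 1 to Table 18** names the same visit, with 7 days either side: "For the biopsies on C2D1". It lets the patient stay on treatment after a refusal, a judgement of significant risk, or an inadequate first sample. It covers that visit and end of treatment.
- **Table 6** (Part C schedule, Cycles 2 and beyond) has a row "Tumor biopsy ¹⁹" marked on Day 1 of the column for Cycle 3 and later, with 7 days either side. Nothing is marked under Cycle 2.
- **Footnote 19 to the Part C schedule tables** gives pre-treatment, Cycle 3 Day 1 with 7 days either side, "and at the time of progression. Each biopsy will be divided into 3 portions". Its continue-treatment clause reads "For the biopsies on C3D1 and EoT, patients will be allowed to continue treatment if" and then lists the same three reasons.
- **The synopsis** says "Biopsies for Part C will be collected at baseline and at the first response assessment". Section 3.1 sets the timing of that assessment: "Response will be assessed every 8 weeks per RECIST 1.1 criteria".

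**The concern.** Two rules for an invasive procedure cannot both be followed. A site working from one table deviates from the other, and a site trying to satisfy both would biopsy the patient twice during treatment.

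The protection attached to the biopsy also differs. Read literally, footnote 19 covers a patient who declines at Cycle 3 Day 1 but not one who declines at Cycle 2 Day 1, and the Table 18 footnote does the reverse.

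On the data side, biopsies called by the same name could come after quite different amounts of treatment.

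**Working it through.** The protocol states no figure to reproduce. The check is whether the stated windows could make the two schedules compatible.

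**Inputs**
- Cycle length: 28 days (Section 3.3).
- Window: 7 days either side, for both visits (Table 18 footnote 1; Table 6 and footnote 19).
- First on-treatment response assessment: every 8 weeks, Day 1 of odd cycles (Section 3.1; footnote 20 to the Part C schedule tables).
- Dosing: 12 KPT-9274 doses per cycle and nivolumab on Day 1 of each cycle (Section 3.1, Table 8).
- Part C size: about 20 patients, at most 10 per dose level (synopsis; Section 9.2.2).

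**Formula.** Study day = (cycle − 1) × 28 + day in cycle.

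| | Cycle 2 Day 1 | Cycle 3 Day 1 |
|---|---|---|
| Study day | (2 − 1) × 28 + 1 = 29 | (3 − 1) × 28 + 1 = 57 |
| Weeks since first dose | (29 − 1) / 7 = 4 | (57 − 1) / 7 = 8 |
| Window | Days 22 to 36 | Days 50 to 64 |
| KPT-9274 doses before it, on schedule | 12 | 24 |
| Nivolumab doses before it, on schedule | 1 | 2 |

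The Part C visit-window table in SAP Section 2.7 gives the same target days, 29 and 57. The dose counts are for a pre-dose biopsy on the target day.

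**Results**
- The targets are 57 − 29 = 28 days apart.
- The gap between the windows is 50 − 36 = 14 days, so the windows cannot explain the difference.
- If both readings were in use, on-treatment biopsies could fall anywhere in a span of 64 − 22 = 42 days.
- The synopsis does not add a third time. The first response assessment is at 8 weeks on Day 1 of an odd cycle, which is Cycle 3 Day 1.

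**Is it a reading error?** Within Table 18 the row and its footnote agree. Table 6 and footnote 19 also agree with each other. A broken table in the PDF would not produce two consistent pairs. None of the five places is amendment-log text, and no visible sentence says which source governs.

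**Neighbouring text**
- The Table 6 column covers Cycle 3 and every later cycle. The imaging row in that column is limited to odd cycles, but the biopsy row carries no limit. In Table 2, for Parts A and B, the later biopsy is limited to Cycle 6.
- The late biopsy is at progression in the timing sentence of footnote 19, but at end of treatment in Tables 7 and 18. The synopsis does not mention it. A patient who stops treatment for a reason other than progression is treated differently by the two rules.

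**The case against.** The best case against the point is that little depends on it. Footnote 19 calls the biopsy an exploratory research procedure. The exploratory objectives are redacted, and the SAP (Sections 1.2.3 and 2) leaves analyses beyond the clinical data to separate plans. No visible endpoint, dose decision or SAP analysis uses the on-treatment biopsy. Section 7.4.1 also refers sites to a Laboratory Manual, in its text on PK sampling for Parts A and B, and such a manual might settle the visit in practice. All of this stands and limits the size of the point. It does not remove the contradiction within the protocol.

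A reader might infer more than the documents support:

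- *That biopsies will be split between week 4 and week 8.* The instructions conflict, but every site could follow the same source. Only the possibility is shown.
- *That Table 18 is the source sites use for biopsies.* Section 7.4.1 introduces it for PK assessments. It does have a biopsy column, which is why the conflict is real, but nothing ranks it above the schedule of assessments.
- *That the paired comparison is part of the rationale for the combination, and that the two times cannot be pooled.* Section 1.3.3 rests on baseline T-cell infiltration, PAK4 and β-catenin correlations and mouse data. It mentions no paired biopsies. Whether the times could be pooled depends on an analysis that is not visible.
- *A number of pairs at each time, such as an even split of about 20 patients.* No document gives a split, and both footnotes foresee missing biopsies.
- *That a patient declining at the visit a footnote omits must stop treatment.* Section 5.2 does not list this among its mandatory reasons. The text leaves the case open.
- *That Table 18 must be wrong because more places name the later visit.* Counting places does not show which visit was intended.

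**Conclusion.** The point holds as an internal inconsistency. Two current rules place the same Part C biopsy at Day 29 and at Day 57, with windows 14 days apart, and the refusal clause follows the split.

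The supportable consequences are possible mistimed or duplicate invasive sampling, an unclear position for patients who decline, and an inconsistent on-treatment sampling time. They concern about 20 patients if Part C runs at its two planned dose levels. The primary safety and RP2D objective is not affected, nor is any sample size.

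The conclusion rests on the 28-day cycle, on the windows as written, and on no unseen document already stating which source governs. It should be corrected, but it does not threaten the trial's main conclusions.

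**What to change.** The sponsor should choose a single on-treatment biopsy visit for Part C. This review does not say which. Then:

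1. Make the synopsis sentence, Table 6, footnote 19, Table 18 and Table 18 footnote 1 all name that visit and its window.
2. State in Table 6 that the biopsy applies to that visit only, not to every later cycle.
3. Tie the continue-treatment clause to that visit, in the same words in both footnotes.
4. Reconcile the late biopsy (progression in footnote 19, end of treatment in Tables 7 and 18), and bring the synopsis into line.

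The cost is text edits to whichever tables, footnotes or synopsis lines do not match the visit chosen. How many change depends on that choice. No procedure is added.
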